Interventions and Duration

This is an open-label, single arm trial of orally-administered C7 in G1D. Subjects will replace a fixed percentage of their daily caloric intake (based on the results of Protocol 1) with C7 for 6 months, undergo full evaluation and discontinuation of treatment at a 6 month visit, and return for an off-treatment follow up visit 3 months after C7 oil discontinuation, for total duration of participation of 9 months. Subjects will undergo

treatment initiation on a 24-hour inpatient basis. During that 24-hr inpatient treatment initiation, subjects will have continuous EEG both to monitor for real-time seizure activity (for safety) and to determine EEG changes (secondary outcome) before, during, and after treatment initiation. Subjects will undergo clinical evaluation, comprehensive blood work, ataxia scale rating, EEG, and neuropsychological testing at baseline, 6 months, and 9 months.

Important: As described in the Proposal and in (1), C7 is always administered as a **replacement** (nor as a source of extra calories for an otherwise unchanged regular diet) to a fraction of the daily calories that are normally consumed by each subject via other nutrients. As such, there is **no caloric impact** of C7 (i.e., the calories that a subject will consume remain unchanged by the addition of C7 to the diet to replace other nutrients – predominantly fat).

Sample Size and Population

Forty-five subjects receiving no dietary therapy (i.e., consuming a normal diet) with a proven (genetically determined) G1D diagnosis will be enrolled. Subjects may be male or female, between the ages of 2 and 35 years old (N=15 per age group: 2 to 6, 7-11, and 12-35 years old), and must be willing to provide assent if they are of age 10-17. Subjects may be English or Spanish speaking. Subjects may be currently taking anticonvulsants or other medications. Subjects must agree not to change their dietary therapy during the trial without consulting with the study team. Subjects must have evidence of abnormal EEG in the last 36 months.

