4. SELECTION AND ENROLLMENT OF SUBJECTS

4.1. Inclusion Criteria

- 4.1.1. Diagnosis of glucose transporter type I deficiency (G1D), confirmed by clinical genotyping at a CLIA-certified laboratory or by PET scan.
- 4.1.2. Stable diet on either a modified Atkins diet or on no dietary therapy (i.e., no dietary therapy for 1 month).
- 4.1.3. Males and females 24 months to 35 years old, inclusive.

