6.3.9. Neuropsychological Evaluations

The assessment battery, administration time, and data source (i.e., parent or child) is included in Table below. The selection of instruments is based on the NIH Workgroup recommendations. Outcome measures were selected based on clinical relevance, satisfactory reliability, established validity, sensitivity to change, minimal practice effect, and feasibility for administration to children with G1D. The battery is complete in that it measures the major domains of cognitive functioning, including intellectual ability, language, attention, working memory, processing speed, emotional and behavioral functioning, as well as adaptive behavior and quality of life. The primary outcome measure will be attention, as measured by performance on a computerized measure (K-

CPT-2 or CPT-3, as described below) for the two older age groups (see **Table B** of the Proposal) and by performance on a working memory composite (Wechsler Working Memory Index [WMI], as described below) for the youngest age group (see **Table B** of the Proposal). The WMI will be the primary outcome measure for the youngest age group because working memory relies heavily on attention—to the extent that it has been conceptualized as “executive attention” (29) and is increasingly viewed as having significant overlap with core attentional processes (30, 31)—and there are no direct, performance-based measures specific to attention that are normed for the youngest subjects in the present study, whereas the WMI is normed for the entirety of the three age groups described in **Table B** of the Proposal. Attention is a core cognitive function that permits access to other areas of cognition (31) and is commonly impaired in association with seizure disorders. Existing research has indicated that dietary interventions have the potential to promote attention functioning in children with G1D (26, 27).

The neuropsychologist or technician will complete the assessment battery. All instruments are age-appropriate and most are recommended as core or supplemental measures by the NIH Workgroup. Rest breaks will be provided.

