Subjects will be administered either the Conners' Kiddie Continuous Performance Test Second Edition (K-CPT 2) (Conners, C. K. (2013). *K-CPT 2: Conners' Kiddie Continuous Performance Test-Second Edition*. North Tonawanda, NY: Multihealth Systems) or the Conners' Continuous Performance Test, Third Edition (CPT-3) (Conners, C. K. (2013). *CPT-3: Conners' Continuous Performance Test-Third Edition*. North Tonawanda, NY: Multihealth Systems) according to age. These tests measure sustained attention and impulsivity; administration takes approximately 7 to 14 minutes depending on age of subject.

Subjects will be administered a Peabody Picture Vocabulary Test, 4th Ed. (PPVT-4) (Dunn, L.M. & Dunn, D.M. (2007). *Peabody Picture Vocabulary Test-Fourth Edition*. Minneapolis, MN: Pearson Assessments) and Expressive Vocabulary Test, 2nd Ed. (EVT-2) (Williams, K.T. (2007). *Expressive Vocabulary Test, Second Edition*. Minneapolis, MN: Pearson Assessments). Combined administration takes approximately 30 minutes, and each test is validated for ages from 2.5 years to adulthood. These tests measure receptive and expressive vocabulary, and incorporate domains of attention, information retrieval, and information expression.

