Parents or caregivers will be asked to complete the Adaptive Behavior Assessment System-Third Edition (ABAS-3) (Harrison, P. & Oakland, T. (2015). *Adaptive Behavior Assessment System-Third Edition*. San Antonio TX: Western Psychological Services) and the Child Behavior Checklist or Adult Behavior Checklist (as age appropriate) (Achenbach, T. M., & Rescorla, L. A. (2000). *Manual for the ASEBA Preschool Forms & Profiles*. Burlington, VT: University of Vermont, Research Center for Children, Youth, & Families, Achenbach, T. M., & Rescorla, L. A. (2001). *Manual for the ASEBA School-Age Forms & Profiles*. Burlington, VT: University of Vermont, Research Center for Children, Youth, & Families, Achenbach, T. M., & Rescorla, L. A. (2003). *Manual for the ASEBA Adult Forms & Profiles*. Burlington, VT: University of Vermont, Research Center for Children, Youth, & Families). These forms take approximately 30 minutes to complete together. Parents or caregivers also will be asked to complete a brief questionnaire (Appendix B: "Patient History Form") that was locally developed to document information related to neuropsychological functioning, including demographic information, other medical history, and academic performance. This data will be collected in order to control for potential confounds affecting performance on the neuropsychological testing battery. This form takes approximately 15 minutes to complete.

The Pediatric Quality of Life Inventory 4.0-Generic Core Scales (PedsQL) (21) will be completed by either the subject or parent/caregiver, depending on age of the subject. At the completion of testing, the neuropsychologist will rate the utility of the completed testing, based on the child's understanding of and ability to do the task. Particularly in the case of our younger subjects, the tests may be validated to their age, but the subject may be too impaired to provide useful testing results.

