The Wechsler Primary and Preschool Scale of Intelligence-4th Edition (WPPSI-IV) is an individually administered, norm-referenced instrument for measuring the intelligence of children aged 2-years, 6-months to 7-years, 3-months. The WPPSI-IV is a revision of the Wechsler Primary and Preschool Scale of Intelligence-3rd Edition (WPPSI-III) instrument recommended by the NINDS Common Data Elements (Neuropsychology) for assessing intelligence (22). The WPPSI-III short-form is recommended for research purposes for obtaining an estimate of a child's intellectual status (Sattler, J. M., & Dumont, R. (2004). *Assessment of children: WISC-IV and WPPSI-III supplement*. La Mesa, CA: Jerome M. Sattler); the short-form of the WPPSI-IV thus is utilized for the present study due to its updated normative data. For each item, the subject will either be asked to define words that are read out loud or respond to a question by choosing a picture from four response options and answer questions that address a broad range of general knowledge topics. The subject will also either view an incomplete matrix and select the response option that completes the matrix or use one- or two-color blocks to re-create a design viewed in a model or picture. The reliability and validity of the selected WPPSI-III short-forms is strong across ages with coefficients ranging from .92 to .93 and .71 to .86, respectively.

The Wechsler Abbreviated Scale of Intelligence-2nd Edition (WASI-II) is an individually administered, norm-referenced assessment of the intelligence of examinees ages 6 years through 90 years. The WASI-II is a revision of the Wechsler Abbreviated Scale of Intelligence (WASI) (Wechsler, D. (1999). *WASI: Wechsler Abbreviated Scale of Intelligence*. San Antonio, TX: Psychological Corporation), recommended by the NINDS for the assessment of intelligence. For each item, the subject will be asked to define words that are read out loud. The subject will also view an incomplete matrix and asked to select the response option that completes the matrix. The overall average reliability for FSIQ-2 (primary index score) is excellent across ages, ranging from .93 to .94. The average test-retest reliability is strong across ages for FSIQ-2, ranging from .89 to .94.

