The Working Memory Index Scale (WMI) is composed of two subtests from either the Wechsler Primary and Preschool Scale of Intelligence-4th Edition (WPPSI-IV WMI): Picture Memory and Zoo Locations; the Wechsler Intelligence Scale for Children, 5th Edition (WISC-V WMI): Digit Span and Picture Span; or the Wechsler Adult Intelligence Scale, 4th Edition (WAIS-IV WMI): Digit Span and Arithmetic. The Working Memory Index Scale (WMI) provides a measure of the examinee's working memory abilities. Young children (ages 2:6 to <6) will be asked to select previously viewed pictures from options on a response page and to place previously viewed animal cards in the previously viewed location on a "zoo" template. Older subjects (ages 6 to 16 years) will be read sequences of numbers and asked to recall the numbers in the same order, reverse order, and ascending order and to select previously viewed pictures from options on a response page. Adult subjects (ages 17+) will be read a sequence of numbers and asked to recall the numbers in the same order, reverse order, and ascending order and to mentally solve a series of arithmetic problems. For the overall normative sample, the average reliability and stability coefficients range from strong to excellent. The WPPSI-IV WMI has an overall average reliability of .91 and an overall average stability of .87. The WISC-V WMI has an overall average reliability coefficient of .92 and average stability coefficient of .82 across ages. The WAIS-IV WMI has an overall average reliability coefficient of .94 and average stability of .88 across ages.

The Purdue Pegboard is a norm-referenced test of manual dexterity of examinees ages 5 years through 89 years. The Purdue Pegboard is recommended by the NINDS for the assessment of fine motor speed and manual dexterity (22). The right-hand (RH) and left-hand (LH) subtests of the Purdue Pegboard provide a time-efficient estimate of these functions. For those two subtests, subjects use only the designated hand to place as many pins in holes as possible within 30 seconds. Test-retest reliability ranges from acceptable to good, ranging from .76 to .89.

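### Entry opens at 24 months but the youngest group's primary measure is listed only from 2:6, so a child aged 24-29 months has no normed baseline and no observable responder status

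*Combined protocol and SAP*

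**What the plan says.** **Eligibility.** Section 4.1.3 admits "Males and females 24 months to 35 years old, inclusive". The synopsis (Sample Size and Population) splits the sample as "N=15 per age group: 2 to 6, 7-11, and 12-35 years old". None of the exclusions in 4.2 removes a child under 2:6.

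**Primary measure.** Section 6.3.9 states: "The WMI will be the primary outcome measure for the youngest age group". Its reason is that no direct performance test of attention is normed for the youngest subjects, whereas "the WMI is normed for the entirety of the three age groups described in Table B of the Proposal".

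**Age range of that measure.** The same section describes the WPPSI-IV, the youngest form, as an instrument for "children aged 2-years, 6-months to 7-years, 3-months". Its account of the WMI reads: "Young children (ages 2:6 to <6) will be asked to select previously viewed pictures". The Schedule of Neuropsychological Testing also starts the WMI at 2:6.

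**Responder and decision rule.** Sections 9.1 and 9.3 define a favorable outcome as a gain of at least 0.5 SD on the age group's primary attention measure, using the instrument's normative SD. Section 9.3 applies a Simon two-stage rule in each age group: stop at 4 or fewer of 7, and do not proceed at 8 or fewer of 13. Fifteen are recruited per group to allow for 15% dropout.

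**Missing data.** Section 9.5 says in general terms that missing data will be multiply imputed.

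**The concern.** The responder definition is a within-subject change on a normed scale, so it needs a normed score before treatment. The plan can enrol and treat a child for whom no such score is scheduled. In a group with decision counts of 7 and 13, a single child can matter, and the sections on sample size and analysis do not address this case. Only the youngest of the three groups is exposed.

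**Working it through.** **1. Age coverage, side by side**

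| Item | Lower age | Where |
|---|---|---|
| Entry | 24 months | 4.1.3; synopsis gives 2 to 6 years for the group |
| WPPSI-IV as an instrument | 2:6 | 6.3.9 |
| WMI, youngest form | 2:6 | 6.3.9; testing schedule |
| K-CPT 2 (attention) | 4 years | 6.3.9; testing schedule |
| PPVT-4 and EVT-2 (vocabulary) | 2:6 | 6.3.9, "each test is validated for ages from 2.5 years to adulthood"; testing schedule |

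The gap runs from 24 months to just under 30 months, and no listed performance test of attention, working memory or vocabulary fills it.

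**2. What can be measured in such a child**

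Entry at 24-29 months puts the child at 24 + 6 = 30 to 29 + 6 = 35 months at the 6-month visit, and at 33 to 38 months at the 9-month visit. The WMI can be given at both. What is missing is the Visit 1 score (Day 1 baseline, and Day 2), so there is nothing from which to measure a change.

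**3. Whether section 9.5 repairs this**

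Multiple imputation borrows from subjects whose value was observed. No child under 2:6 in this trial can have an observed baseline WMI, so the imputed value would be extrapolated entirely from older children. Section 9.3 also gives no way to turn several imputed data sets into a count for the 7-subject and 13-subject rules.

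**4. The plan's own figures**

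Inputs from 9.3: null rate 0.50, alternative 0.80, continue if at least 5 of 7, success if at least 9 of 13.

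P(success) = sum over x = 5, 6, 7 of P(Bin(7, p) = x) × P(Bin(6, p) ≥ 9 − x).

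- p = 0.80: 0.2753 × 0.9011 + 0.3670 × 0.9830 + 0.2097 × 0.9984 = 0.818.
- p = 0.50: 0.1641 × 0.3438 + 0.0547 × 0.6562 + 0.0078 × 0.8906 = 0.099.

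These agree with the stated 80% power and 0.1 type I error. The design arithmetic in 9.3 is not in question.

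**5. One scenario for the size of the effect**

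Assumptions: 15 places are fixed; k of them go to children aged 24-29 months; 15% dropout is complete before the primary score; nothing is imputed; the stage-one 7 are all scored; the final cut-off of 9 is kept when fewer than 13 scores exist; scores beyond 13 are not used; fewer than 9 scores means no success.

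Power at p = 0.80 by number of scores: 13 gives 0.818; 12 gives 0.757; 11 gives 0.617; 10 gives 0.376; 9 gives 0.134.

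The number of scores M follows Bin(15 − k, 0.85). Average power = sum over m of P(M = m) × power(min(m, 13)).

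| k | Expected scores, (15 − k) × 0.85 | P(M ≥ 13) | Average power |
|---|---|---|---|
| 0 | 12.75 | 0.60 | 0.75 |
| 1 | 11.90 | 0.36 | 0.68 |
| 2 | 11.05 | 0.12 | 0.57 |

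For k = 1: 0.357 × 0.818 + 0.291 × 0.757 + 0.206 × 0.617 + 0.100 × 0.376 + 0.035 × 0.134 = 0.68.

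The k = 0 row is the effect of dropout alone. It is a separate matter and no part of this point, which concerns only the step down from that row.

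**6. A milder scenario**

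If the primary score is the Visit 1 Day 2 test and nobody has dropped out by then, one or two such children leave 15 − 1 = 14 or 15 − 2 = 13 scores. The planned 13 is met and power stays at 0.82.

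**7. How many such children**

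The documents give no age distribution. Purely as an assumption, an even spread of entry ages from 2:0 to 6:11 would put 6 of 60 months, or 10%, below 2:6, which is 1.5 of 15. The true number may be zero.

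**The case against.** **The plan is not silent on missing data.** The imputation sentence stands in the primary-aim paragraph of 9.5 and, read literally, covers an absent baseline. A reader might infer that the documents offer no rule at all, and that would be wrong. What stands is narrower: a rule exists, but it does not suit a baseline that no child of that age can have.

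**The power figures depend on open choices.** Section 9.1 places the 6-month responses among the remaining outcomes, which suggests an acute primary score, while 9.2.1.1 names both acute and long-term improvement. With an acute primary the loss may vanish, as step 6 shows. This objection is sound, and the figures are therefore one scenario only.

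**A reader might infer that an untested child counts as a failure at stage one.** No passage says so. Section 9.3 speaks of accrual, but it reaches 13 from 15 by taking off dropout, which suggests subjects remaining after losses.

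**A reader might infer that the norming statement in 6.3.9 is false.** It refers to Table B of the Proposal, which is not among the documents. If Table B starts at 2:6, the statement is correct and only the synopsis and 4.1.3 need changing.

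**The plan already expects some unusable results.** Section 6.3.9 warns that "the subject may be too impaired to provide useful testing results". That concerns impairment on a test valid for the child's age, so it does not cover a test that is not listed for that age.

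**Conclusion.** The conflict between the entry age and the age range of the youngest group's primary measure is certain and can be read directly from the protocol. For a child aged 24-29 months at entry, the 0.5 SD responder status cannot be observed and could only come from an imputation with no observed baseline at that age behind it.

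The practical effect is uncertain. It depends on how many such children enrol, whether they occupy places among the 15, and which time point is primary. Under the assumptions of step 5, power falls from 0.75 to 0.68 with one such child and to 0.57 with two; under those of step 6 it does not fall. The documents do not support calling this an established loss of power, and the other two age groups are untouched. It ranks between minor and should-fix: a small inconsistency that is cheap to remove.

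**What to change.** Reconcile the synopsis and 4.1.3 with the age ranges in 6.3.9 and its testing schedule, in one of two ways.

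- **(i) Raise the floor.** Set the lower age at 30 months at baseline in 4.1.3 and the synopsis. Cost: safety, EEG and caregiver-rated data from children aged 24-29 months are lost, or delayed by up to 6 months. Safety in children is a stated aim, and section 2.1 argues that the developmental window closes.
- **(ii) Keep 24 months and limit the count.** Keep younger children for safety, EEG and caregiver-rated outcomes. State in 6.3.9, 9.3 and 9.5 that only children aged 2:6 or older at baseline count toward the 7, the 13 and the 15 of the youngest group; that younger children are enrolled outside that count; and that their primary outcome is not applicable and is not imputed. Cost: those children do not inform the go/no-go decision, and any who enrol come on top of the planned 45.

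Under either option, check the norming statement in 6.3.9 against Table B. Both are changes of protocol wording. Neither guarantees 13 scores, because each only returns the group to its dropout-only position (the k = 0 row).

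The change of WMI form at age 6 in 6.3.9 and the testing schedule is a different question and should be raised separately.

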The EVT-2 is an individually administered, norm-referenced instrument that assesses expressive vocabulary and word retrieval for children and adults ages 2 years 6 months through age 90 years. The EVT-2 provides two parallel forms A and B, and is co-normed with the PPVT-4. Alternate form reliability across ages is excellent ($M=.87$) as is test-retest reliability across ages ($M=.95$).

Validity and reliability of the PPVT-4 and EVT-2 may be limited for examinees whose primary language is not English or Spanish, but this is predicted to affect a very small number of subjects. At present, all North American patients in the registry have identified English as their primary language. With any neuropsychological measure, individual factors such as language and overall degree of impairment may result in reduced utility of results in select cases, as previously acknowledged on Page 22 of this Protocol.

The Adaptive Behavior Assessment System-Third Edition (ABAS-3) provides a comprehensive norm-referenced assessment of the adaptive skills of individuals ages birth to 89 years. The scale yields assessment of 10 individual adaptive behavior domains (e.g., Self-Care, Home Living) and aggregates into Social, Conceptual, Practical, and General Adaptive Composites. Test-retest reliability for the General Adaptive Composite across ages ranges from .82-.89 and inter-rater reliability across ages ranges from .83-.85.

The Child Behavior Checklist for Ages 1 ½ to 5, Child Behavior Checklist, and Adult Behavior Checklist are parent/caregiver rating scales that assesses competencies, adaptive functioning, and behavioral, emotional, and social problems from age 1½ to over 90 years. Test-retest reliability is excellent, with coefficients for Total Problems scales for the parent/caregiver form falling at .90 for the preschool version, .94 for the school age scale, and .92 for the adult version of the rating scale. Stability correlations are also acceptable at 12 months for the preschool ($r=.76$) and school age ($r=.81$) version, and 2-year stability of the adult version falling at an acceptable level ($r=.67$).

The PedsQL 4.0- Generic Core Scales is a modular approach to measuring health-related quality of life (HRQOL) in healthy children and adolescents and those with acute and chronic health conditions. The PedsQL 4.0 Generic Core Scales consist of 23 items and

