9.3. Sample Size and Accrual

We estimated the sample size using the primary outcome (attention) for each of three age groups. The same method will be applied for sample size estimation in each of three age groups. An improvement of 0.5 SD or more on the primary attention measure

after the administration of C7 is considered a favorable outcome. This study will yield data that allow a clear go/no-go decision regarding whether C7 should proceed to an efficacy trial: If a favorable outcome occurs in less than 50% of subjects, we will recommend that C7 not proceed to an efficacy trial. If a favorable outcome occurs in at least 80% of subjects, we will recommend that C7 proceed to an efficacy trial.

The sample size was estimated using Simon's optimal two-stage design (24). The null hypothesis that the proportion of favorable outcome is 50% will be tested against a one-sided alternative hypothesis that the proportion of favorable outcome is 80%. In the first stage, 7 subjects will be accrued. If there are 4 or fewer favorable outcomes in these 7 subjects, the study will be stopped, and we will recommend that C7 not proceed to an efficacy trial. Otherwise, 6 additional subjects will be accrued for a total of 13 subjects. If 8 or fewer favorable outcomes are observed in 13 subjects by the end of stage two, then no further investigation of C7 is warranted. This design yields a type I error rate of 0.1 and power of 80% when the true favorable outcome occurs in 80% of subjects. We plan to recruit 15 subjects with an expected 15% dropout rate resulting in 13 subjects for each age group. That is, we will recruit a total of 45 subjects for this protocol.

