9.5. Data Analyses

Summary descriptive statistics: For normally distributed, continuous data, means and standard deviations will be used to describe the demographic and clinical characteristics of the patient population participating in the study and medians and semi-interquartile ranges will be used to describe characteristics of the patient population when the data are continuous, non-normally distributed. For categorical or dichotomous variables, the frequency or the proportion will be reported.

Primary Aim: The primary aim is demonstrating the benefit of C7, as measured by a change in performance on the primary attention measure for each age group. The proportion of subjects who achieved favorable outcome will be estimated along with the corresponding 95% confidence interval using an exact binomial method. We will also investigate if there will be significant differences in the proportions of favorable outcomes among three age groups using Fisher's exact test. We will make every effort to minimize the missing data. We expect minimal amount of missing data. If missing data occurs, missing data will be imputed using multiple imputation techniques.

Generalized estimating equation (GEE) analysis will be used to examine if C7 positively affects other neuropsychological (e.g., IQ, language, processing speed) and neurological performance, such as ataxia over time (baseline, 6 months, and 9 months).

Secondary Aim: A secondary aim is to evaluate the effect of C7 supplementation of a regular diet on an EEG activity and to evaluate the safety of C7 supplementation. EEG will be analyzed in 3 ways (spike-wave duration, total number of seizures and background of the EEG as described above). GEE analysis will be used to examine if there are significant changes in EEG activity and safety over time. GEE analysis will be also conducted to investigate whether attention neuropsychological scores correlate with the EEG findings.

Study end. Statistical analyses at the end of the study will examine the initial measures at baseline, 6 months, and 9 months. Repeated measurement data will be analyzed using the generalized estimating equation (GEE) approach. The GEE method has been widely used for the analysis of repeated measurement data because of its robustness to random missing and misspecification of the true correlation structure.

SAS V9.4 (SAS Institute, Inc. SAS V9.4, Cary, NC, 2014) will be used to analyze the data.

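### The plan does not say how an unusable primary attention test enters the responder count, and it does not require a scorable baseline

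*Combined protocol and SAP*

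**What the plan says.** - **Rating.** Under 6.3.9, once testing is finished, "the neuropsychologist will rate the utility of the completed testing". The basis is the child's understanding of the task and ability to do it. No scale, cut-off or consequence is given.
- **Untestable subjects are expected.** The same section warns, especially for younger subjects, that "the subject may be too impaired to provide useful testing results". It later says that language and degree of impairment "may result in reduced utility of results in select cases".
- **Blinding.** The Synopsis describes an open-label, single-arm trial. Blinded reading is described only for the EEG (6.3.12).
- **Entry.** Nothing in 4.1, 4.2 or the screening steps in 6.2.1.1 asks for a usable score on the primary measure. Exclusion 4.2.9 concerns dementia and degenerative disease, not testability. Section 4.1.3 admits children from 24 months. In 6.3.9 the youngest group's primary measure, the Working Memory Index (WMI), is given from 2 years 6 months, yet the same section describes the WMI as normed across all three age groups.
- **Outcome and decision rule.** Section 9.1 defines a favourable outcome as a gain of at least 0.5 normative SD. Section 9.3 applies a Simon two-stage rule in each age group: "If there are 4 or fewer favorable outcomes in these 7 subjects, the study will be stopped", and the result is negative "If 8 or fewer favorable outcomes are observed in 13 subjects by the end of stage two".
- **Missing data.** Section 9.5 says: "If missing data occurs, missing data will be imputed using multiple imputation techniques". It does not mention the utility rating, or say how imputed values would enter the two stage counts.

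**The concern.** A 0.5 SD gain can be judged only with a scored baseline and a scored follow-up. The utility rating is made after the performance and depends on ability to do the task, which is close to the attention outcome itself. A child who cannot do the task while on C7 has not shown improvement. If that test is set aside as not useful, an unfavourable result can leave the observed data, and the people making the judgement are not described as blinded to visit. At baseline the gap works the other way: a subject with no scorable pre-oil test can be enrolled and never classified, or can sit among the 13 as an automatic failure. With 13 subjects per group, one or two such cases can change a go/no-go result.

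**Working it through.** **Inputs from 9.3.** Null rate 0.50, tested against a "one-sided alternative hypothesis that the proportion of favorable outcome is 80" percent. Stage 1: 7 subjects, continue with at least 5 favourable. Final: 13 subjects, at least 9 favourable. Fifteen are recruited per group with 15% dropout expected. The documents give no rate of unusable tests, so every such rate below is an assumption.

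**1. The plan's own figure.** P(go) = sum over x = 5, 6, 7 of P(Bin(7, p) = x) × P(Bin(6, p) ≥ 9 − x).
- p = 0.5: 0.1641×0.3438 + 0.0547×0.6563 + 0.0078×0.8906 = 0.099.
- p = 0.8: 0.2753×0.9011 + 0.3670×0.9830 + 0.2097×0.9984 = 0.818.

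This agrees with the statement "This design yields a type I error rate of 0.1 and power of 80" percent.

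**2. Unusable follow-ups imputed.** Let a fraction q of unfavourable tests be treated as missing. The favourable rate among usable tests is then r = 0.5/(1 − 0.5q). If each missing test is imputed as favourable with probability r, each subject counts as favourable with probability 0.5 + 0.5q × r, which equals r. No replacement subjects are needed. Putting r into the formula of step 1:

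| q | r | False-go probability |
|---|---|---|
| 0 | 0.500 | 0.099 |
| 0.10 | 0.526 | 0.135 |
| 0.25 | 0.571 | 0.214 |
| 0.40 | 0.625 | 0.338 |

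**3. Unusable follow-ups dropped, refilled only within the 15.** Each enrolled subject is evaluable with probability 0.85 × (1 − 0.5q), and an evaluable subject is favourable with probability r. The number evaluable is binomial out of 15, and at most the first 13 are used. The thresholds stay at 5 of the first 7 and 9 in total. The false-go probability is 0.078 at q = 0, and 0.090, 0.106 and 0.118 at q = 0.10, 0.25 and 0.40.

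**4. Untestable entrants.** With a fraction u untestable, the chance of at least 13 evaluable subjects is P(Bin(15, 0.85(1 − u)) ≥ 13).
- u = 0 (planned dropout alone): 0.60.
- u = 0.10: success probability 0.765, chance 0.28.
- u = 0.20: success probability 0.68, chance 0.10.

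If one untestable subject stays among the 13 as a failure, power at a true 80% in the others is 0.612 when that subject falls in stage 1 and 0.757 when in stage 2. With random placement it is (7/13)×0.612 + (6/13)×0.757 = 0.679, against 0.818.

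**The case against.** The strongest objection is that a reader might infer the plan discards low-rated tests, and the documents do not say so. The rating could be purely descriptive, with every scored test counted. That stands: the defect is a missing rule, not a stated exclusion.

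A reader might also infer that an unblinded tester rates his or her own session. Section 6.3.9 lets a technician give the battery, so tester and rater may differ, and the older groups' computerised score is not altered by the rating. That also stands. What remains is that no blinding is described for either role.

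Third, the plan has no provision for replacing a discarded test. If discarded tests are simply removed, with recruitment held at 15 and 15% dropout, the false-go probability stays close to the nominal 0.1 (step 3). This is correct for the drop-and-refill route. It does not cover imputation, which is the only missing-data rule in the plan and reaches the larger figures without any replacement.

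Finally, the low chance of 13 evaluable subjects should not be blamed on testability alone. Planned dropout already brings it to 60%.

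**Conclusion.** The concern holds as a gap in the rules. The plan does not say how a low utility rating or an untestable baseline enters the 4/7 and 8/13 counts. Under the plan's stated imputation, treating such follow-ups as missing would favour C7.

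The size depends on how the gap is filled. The false-go probability per group is about 0.135 to 0.338 if 10% to 40% of unfavourable tests are imputed at the usable-test rate, and about 0.090 to 0.118 if they are dropped within the cap of 15. The upper figures are not the error rate of the plan as written. They assume that a low rating means missing, that the loss falls only on unfavourable tests, and that the imputation model carries no information about why the test was unusable. The 10% and 20% untestable rates are likewise illustrative. The point should be settled before the counts are made, because the rule is cheap to write and bears directly on the go/no-go decision.

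**What to change.** - **9.1 and 9.5.** State that once a subject has a scorable baseline, a follow-up primary test that is unusable or cannot be done counts as not favourable in the 4/7 and 8/13 rules, and is neither dropped nor imputed. At a true 50% rate with all the loss among unfavourable tests, this keeps the false-go probability at 0.099.
- **6.3.9 and 9.3.** Count a subject toward the 7 and 13 only if the Day 1 pre-oil test on the age group's primary measure gives a normed, scorable result. Use criteria fixed in advance and decide before C7 starts. An objective scorability condition is better than using the unscaled utility rating as a gate, which would add discretion over who counts.
- **4.1.3 and 6.3.9.** Reconcile the 24-month entry age with the WMI's lower limit of 2 years 6 months, and with the statement that the WMI is normed for all three groups.

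The cost is protocol wording, since the Day 1 test already exists. The result would apply to testable patients, a few more subjects may need screening, and the responder rate becomes slightly conservative where a true responder has an unusable follow-up.
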